Participants will be recruited through convenience sampling of those working or training on the ICUs on days when it is possible to run the tasks. Individuals will not be recruited more than once.

Each participant will be given a numeric study ID and parameters recorded against this including:

- Job title- Consultant/fellow
- Gender- Male/female/prefer not to say
- Age- 21-30/31-40/41-50/51-60/61+
- Number of CVCs that they have previously inserted - <10, 10-50, >50).
- Time since last simulation training- 1 week/ 2-4 weeks/ 1-2 months / 3-6 months / 7-12 months / 1-2 years / >3 years

STUDY OUTCOMES

Primary Outcomes

Mean and standard deviation (accuracy) of time intervals measured.

Accuracy of retrospective recall of trends in monitored observations.

Secondary Outcomes

Impact of experience on time perception and monitoring changes.

STUDY PROCEDURES

Recruitment of participants

Participants will be provided with the information sheet appended and given the opportunity to ask any questions before consenting to the study. They will be asked to sign the appended consent form. Their consent forms will be in no way linked to the data collected such that participants could be identified from their data.

Randomisation

Block randomisation will be used to ensure even distribution of individuals at each grade of experience between the allocation groups. A block size of 4 will be used with 2 strata (grade= Consultant, Other). The randomisation list was determined by an online randomisation service ^[27]. The list generated is included as an appendix.

Two parts of the experimental process are randomised.

The first is the order in which the administrative and technical tasks are performed- this is randomised to remove the impact of primacy-recency impacts as well as task training through more practice with the timing apparatus.

The second is the scenario displayed on the monitor. As we are asking participants to identify a trend, randomisation to an increasing or decreasing trend reduces the likelihood of guessing the correct answer.

The study cannot be blinded at the time of data capture given the significant obvious differences between the tasks.

Study procedure

Structure

The overall structure is outlined below with further detail on each section provided in the following section.

Section order	Comment
Consent and discussion	To ensure valid consent and answer queries

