You have been asked to insert a femoral CVC and have already prepared your equipment.. The line is not flushed. You are already wearing the appropriate sterile gown. Please only use steristrips and dressings, with no sutures, to secure the line to the mannequin. Please document the procedure on the paper provided when you have completed insertion of the line.

I am the nurse in the next bedspace, if at any point you want to make a clinical intervention please continue with the task and verbalise anything you would like me to do.

As before, from when I ask you to begin, please press the foot pedal every 10 seconds, trying to be as accurate as possible. The task will last for several minutes.

Given that this is a simulated mannequin please take all the time you need to familiarise yourself with the ultrasound appearance of the vessels before telling me you are ready to begin.

Events during the task:

Same as for the administrative task.

End point

6 minutes or completion of task documentation.

At the end of the task, progress through the checkpoints below will be noted by the experimenter:

1. Equipment preparation / line flushing
2. Cleaning of the procedure site
3. Initial ultrasound scan
4. Needle manipulation
5. Guide wire insertion
6. Tract dilation
7. Line insertion
8. Line suturing
9. Line dressing
10. Documentation completed

The participant will be asked for the time period they believe has elapsed between the first pedal press and the last.

Post- task review

Following completion of the second task the participant will immediately be asked the following questions:

“Did you see anything of note on the monitor aside from the desaturation” - their yes/no answer is recorded.

“If there were changes in the blood pressure did you notice a fall or a rise” - their rise/fall answer is recorded.

Was the extent of the fall/rise in systolic pressure: 5, 10,15, 20 or 25 mmHg- their selection is recorded.

Which of the tasks did you find more challenging? And why?

They are then asked to describe their subjective experience- “how were those tasks for you?”

They are then asked- “How would you describe your familiarity with EPIC order requesting?”- Very, somewhat, limited, none

They are then provided with the questionnaire from the appendix.

Measurement tools used

- For each experimental run there are 2 variables
 - The task order- administrative or technical completed first

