 - The trend in monitored observations- increasing or decreasing blood pressure in the second task

The following parameters are measured during both tasks:

- Timestamps of foot pedal use by the participant
- Retrospective recall of total elapsed time
- Time to complete task/progress at experiment end
- Question responses

Following completion of the tasks the data collected can be analysed as below.

Time interval analysis:

- Intervals between pedal presses are extracted for each scenario (timing control/administrative/technical tasks)
 - Derive: min/max/mean/interquartile range/standard deviation for each case
- Comparison of the individual’s retrospective perceived elapsed time with actual elapsed time. Reported as percentage error of actual elapsed time.

This will allow the following results to be reported:

- Mean deviation for each individual from their baseline in each of the tasks.
- Change in retrospective perceived elapsed time compared to actual elapsed time.
- Distribution of timing in the control task for each individual.
- Paired t-test comparison to test if there are significant differences in time interval distribution for each individual between control, administrative and technical tasks.
- Overall proportion of participants showing significant deviation from their own baseline in each of the administrative and technical tasks
- Population limits/mean
- Comparison of the mean perceived time interval between subgroups
 - By task order

- By time within task (split into thirds- 2 minutes each)
- By grade
- By number of CVCs previously inserted
- By first 25% vs last 25% of participants

Monitor trend perception analysis:

Each participant will provide question answers from immediately after the second task.

This will allow the following results to be reported:

- Rationale
 - The first question “Did you see anything of note on the monitor” is chosen to highlight inattentive blindness and is asked immediately to avoid any impact from the role of memory or priming from other questions asked.
 - This will be reported as proportion who noted a change
 - The subsequent questions are asked to elicit responses from those who observed the trend but are not sufficiently confident in their recall to report it.
- From the responses the following can be derived:
 - Correct identification of the blood pressure trend- reported as proportion of participants correct

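### The first post-task question records only yes or no to seeing anything of note, so reporting it as the proportion who noted a change can misclassify participants in both directions

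*Combined protocol and SAP*

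**What the plan says.** Under Post-task review, the first question is "Did you see anything of note on the monitor aside from the desaturation", and "their yes/no answer is recorded". The second is "If there were changes in the blood pressure did you notice a fall or a rise", with rise or fall recorded. The third asks for the size of the systolic change. The written questionnaire in the Appendix follows.

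Under Monitor trend perception analysis, the Rationale says the first question "is chosen to highlight inattentive blindness and is asked immediately to avoid any impact from the role of memory or priming" from other questions. Of its result it says: "This will be reported as proportion who noted a change". The later questions are there to "elicit responses from those who observed the trend but are not sufficiently confident in their recall to report it". They feed a different result: "Correct identification of the blood pressure trend- reported as proportion of participants correct".

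The primary outcome in this domain is "Accuracy of retrospective recall of trends in monitored observations". The proportion who noted a change is not named as primary.

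**The concern.** Seeing something of note and noting a change are different things. A yes is counted whatever prompted it, and no rule ties it to blood pressure or to the later answers. A no is counted as unaware even if the participant saw the drift and judged it unimportant. Because the second question names blood pressure, no later analysis can reconstruct what the participant would have said unprompted.

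The plan chose this item to show inattentional blindness free of priming. If its label and its content diverge, the comparison between those who did the technical task second and those who did the administrative task second may not show what it appears to show.

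**Working it through.** **1. Can a yes refer to something else?** The question excludes the desaturation, and Scenarios A and B hold all parameters other than blood pressure constant. A false yes therefore needs either a misperceived parameter or a remark on a static value. The scenarios supply one such value. The first task shows a steady 90/50 (Administrative task, Events during the task), while Scenario B opens at 75/48. A participant could note the lower opening pressure, see no trend, and still be counted.

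**2. Can a no hide someone who saw the drift?** The administrative task section gives 5th centiles of 65 + (2 × 2) = 69 systolic and 50 + (2 × 2) = 54 mean; both sums are right. The low end of the drift is 75/48 (55): systolic 6 above its centile, mean 1 above. There is no alarm, and Scenario B rises to 90/50. A clinician could see the drift and not think it worth reporting. The analysis section gives the low value as 70/48 (55) instead. That conflict needs reconciling, but 70 is also above 69, so the point stands either way.

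**3. Do the later items recover the answer?** The oral follow-up names blood pressure and records only rise or fall, so a pure guess is right about half the time. If 30% truly noticed and the rest guessed, 0.30 + 0.70 × 0.5 = 65% would be correct. The written item adds options for no change and no recall, but it comes after the prompt.

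**4. Size, for illustration only.** The plan states no sample size, alpha or expected proportion, so there is no figure to reproduce. Inputs:
- 20 per group, the most available from a pool of around 40 split by which task came second (Study population; Monitor trend perception analysis)
- Fisher's exact test (Statistical methods), two-sided at 0.05 (assumed)
- true noticing *p* of 70% v 30% (assumed)
- *f*, the share of non-noticers who say yes, and *m*, the share of noticers who say no (both assumed)

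Observed yes rate = *p*(1 − *m*) + (1 − *p*)*f*. With equal *m* and *f* in both groups, the difference is multiplied by (1 − *m* − *f*). Power is by exact enumeration.

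| *m* | *f* | Observed | Difference (points) | Power |
|---|---|---|---|---|
| 0 | 0 | 70% v 30% | 40 | 0.60 |
| 0 | 0.05 | 71.5% v 33.5% | 38 | 0.55 |
| 0 | 0.10 | 73% v 37% | 36 | 0.50 |
| 0 | 0.20 | 76% v 44% | 32 | 0.43 |
| 0 | 0.40 | 82% v 58% | 24 | 0.28 |
| 0.10 | 0.10 | 66% v 34% | 32 | 0.39 |
| 0.20 | 0.20 | 62% v 38% | 24 | 0.21 |

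For the row *f* = 0.20: 0.70 + 0.30 × 0.20 = 0.76 and 0.30 + 0.70 × 0.20 = 0.44.

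**5. Unequal error rates.**
- *Widening.* With *m* = 0 and false-yes rates of 30% in the 70% group and 0% in the 30% group, the observed rates are 0.70 + 0.30 × 0.30 = 79% v 30%, a gap of 49 points instead of 40.
- *Artefact.* With true noticing of 50% in both groups, *m*/*f* of 0.1/0.2 in one gives 0.45 + 0.10 = 55%, and 0.3/0.1 in the other gives 0.35 + 0.05 = 40%. That is a 15-point gap with no true difference.

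**The case against.** The best defence is that blood pressure is the only thing programmed to change apart from the excluded desaturation, so most yes answers probably do refer to it. That stands. A reader might infer that the proportion certainly counts the wrong people, but the documents support only that it can.

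A reader might also infer that this is the trial's only unprompted measure of awareness. The Introduction and the scenario descriptions say the study will capture when a change is noticed, and participants are told to voice any intervention they want. However, the parameters listed under Measurement tools used do not include that time point, so how it would be recorded is unclear.

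Nor is the proportion uninterpretable. The follow-up questions and written questionnaire are put to everyone. The items on heart rate and respiratory rate can identify some participants who believed another parameter moved. Trend identification, which is closer to the primary outcome, is reported separately. These items help, but all come after blood pressure has been named.

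Finally, one might infer that misclassification must dilute the task difference. That follows only if error rates are equal in the two groups, which nothing in the plan establishes.

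The plan says it is a pilot not expected to be adequately powered. The power figures therefore only show scale; the point rests on what the proportion means.

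**Conclusion.** The point holds as a gap between label and content in one non-primary proportion. As written, the plan reports a bare yes as noting a change and discards the evidence that would show whether it was one. Both directions of error are plausible on the protocol's own monitor values, but their frequency is unknown.

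Under the assumptions above, equal false-yes rates of 5% to 20% take a true 40-point difference to between 38 and 32 points, and power from 0.60 to between 0.55 and 0.43. Unequal rates can push the difference either way. The change is worth making before data collection because the unprompted answer cannot be recovered afterwards.

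**What to change.** Keep the yes/no question as it is. If the answer is yes, ask only the neutral question *What did you see?* and record the reply verbatim before blood pressure is mentioned. Avoid asking whether any value changed or in which direction, because that is itself a prompt.

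In the analysis:
- Define noting the change as spontaneously naming a change in blood pressure.
- Report the raw yes proportion separately, labelled as having seen something of note.
- Cross-tabulate both with the later trend answers. This shows who answered no but afterwards reported the drift. Read the oral rise/fall answer with its roughly 50% guessing rate in mind, alongside the written item.
- Leave direction with the existing trend-identification outcome.

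The cost is a few seconds per participant and a simple coding rule. The monitor scenarios do not change.

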However there is a key difference in the clinical populations found in the literature, surgeons have an operative team and are not responsible for patient monitoring while operating. Likewise anaesthetists are usually accompanied by an ODP and are not undertaking practical skills in isolation.

We were not able to find any published literature addressing attention and perception during ICU procedures.

What does this research add?

There is no published experimental data investigating how clinician time perception and attention are impacted by performing tasks in an IC environment. There is an expectation that time perception and attention are preserved, such that clinicians can insert central access as a sole practitioner. Should our investigation show that attention is impacted then this could inform changes to practice as to how monitors and/or additional staff members are utilised during procedures and clinical tasks and how practitioners are trained to undertake them.

AIM(S) OF STUDY

- To investigate the relationship between task type, perceptual loading and attention in an ICU environment
- To investigate the relationship between task type, perceptual loading and time perception in an ICU environment
- To examine if the extent of these effects (if any) are affected by clinician role and/or experience

OBJECTIVES

The objective of this study is to measure clinician awareness of time progression and monitoring trends in the clinical environment during 2 different types of task.

HYPOTHESIS

H₀: Task type has no impact on clinician time perception or awareness of monitoring trends.

H_A: In the technical task clinician time awareness is more inaccurate than in the administrative task

H_B: In the technical task clinician awareness of monitoring trends is impaired compared to in the administrative task

STUDY DESIGN

STUDY SETTING/LOCATION

This will be a single-centre study undertaken in the Intensive Care Units at Great Ormond Street Hospital. The study tasks will be run in the simulation room on the general Paediatric ICU.

STUDY POPULATION

Participants will be recruited from the group of ICU junior/senior tier fellows and Consultants working on the ICUs at Great Ormond Street Hospital. This comprises a pool of around 40 staff members. All staff members are routinely involved in the care of patients in a PIC environment.

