Appendix

Administrative task- instructions and task material

Instructions

You are the admitting doctor for a newly arrived patient.

Please request the admission PIM-TS investigations as on the sheet provided.

Investigations required

Sophie Digby

432 458 6644

14/8/2019

NKDA

Weight: 12kg

Investigations all to be completed within 24 hours, you carry bleep 1234:

- FBC
- UE, Bone, LFT, GGT, Mg
- LFTs, CRP, ESR, ASOT, Vitamin D, PTH
- Coagulation profile-not on anticoagulation, Group & Save
- Blood film
- D-Dimers, Ferritin, Immunology save serum, Triglycerides, LDH, CK
- Trop-I, NT-proBNP
- Amylase, Lipase, faecal calprotectin, urine albumin:creatinine ratio
- ECHO- Discussed with [name], Reason: Other
- Chest X-ray, AXR, Abdominal USS, EEG
- Diagcore SARS-CoV-2
- Respiratory Viral screen
- COVID serology
- Stool M,C&S, Stool enteric virus panel, and stool SARS-CoV-2 PCR
- Blood M,C&S, urine M,C&S, BAL M,C&S, throat culture
- Viral Blood PCR: EBV, CMV, Adeno, Enterovirus, HIV
- Blood PCR: Pneumococ., Meningococ., Group A strep, Staph A
- Lymphocyte subsets (TBNK)

Post task questionnaire

1. Overall the blood pressure:

Rose [] Stayed the same [] Fell [] I don't recall []

2. Overall the heart rate:

Rose [] Stayed the same [] Fell [] I don't recall []

3. Overall the respiratory rate:

[figure not shown]
Rose [] Stayed the same [] Fell [] I don't recall []

4. Mark the initial systolic blood pressure on the line below (with an x):

[figure not shown]
I do not recall the value []

5. Mark the initial mean blood pressure on the line below (with an x):

I do not recall the value []

6. Mark the final systolic blood pressure on the line below (with an x):

I do not recall the value []

7. Mark the final mean blood pressure on the line below (with an x):

I do not recall the value []

Randomisation list^[27]

Block sizes: 4

Stratification factors: Role (Consultant, Other)

Participant number	Monitor scenario	Role	
		Consultant	Other
1	A	Administrative first	Administrative first
2	B	Administrative first	Technical first
3	A	Technical first	Technical first
4	B	Technical first	Administrative first
5	A	Administrative first	Administrative first
6	B	Technical first	Administrative first
7	A	Administrative first	Technical first
8	B	Technical first	Technical first
9	A	Administrative first	Administrative first
10	B	Technical first	Technical first
11	A	Technical first	Technical first
12	B	Administrative first	Administrative first

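### Correct identification of the blood pressure trend, one measure of the trend-recall primary outcome, has no named scoring item; scored on the verbal rise/fall question, it would mix noticing with guessing

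*Combined protocol and SAP*

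**What the plan says.** Primary Outcomes lists "Accuracy of retrospective recall of trends in monitored observations". The related hypothesis, H_B, is that "In the technical task clinician awareness of monitoring trends is impaired compared to in the administrative task".

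Monitor trend perception analysis sets out several measures for this outcome. The open question about the monitor has its own: "This will be reported as proportion who noted a change". A second is "Correct identification of the blood pressure trend- reported as proportion of participants correct", derived from the responses in general. Others cover the absence of trends in other parameters and the accuracy of the recalled pressures.

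Two questions could supply the second measure:

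- **Verbal, in the Post-task review.** After the open yes/no question the participant is asked "If there were changes in the blood pressure did you notice a fall or a rise", and a rise/fall answer is recorded. Next comes "Was the extent of the fall/rise in systolic pressure: 5, 10,15, 20 or 25 mmHg- their selection is recorded". Neither is restricted to those who answered yes to the open question. The stated purpose is: "The subsequent questions are asked to elicit responses from those who observed the trend but are not sufficiently confident in their recall to report it".
- **Written, item 1 of the Post task questionnaire (Appendix).** The options are "Rose [] Stayed the same [] Fell [] I don't recall". It is completed after all the verbal questions.

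Randomisation says that the monitor scenario (A falling, B rising) is randomised so that a correct guess is less likely. In the Appendix list the scenario column reads A, B, A, B through all 20 rows.

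**The concern.** Two analysts following this plan could score different questions and report different proportions correct from the same participants. The plan also has no rule for *Stayed the same*, *I don't recall*, a blank, or verbal and written answers that disagree.

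The choice of question matters because the verbal item offers only two answers and its size follow-up has no zero. Someone who saw nothing but answers leaves the same verbal record as the unsure observer whom the follow-up is meant to reach. A plain proportion correct on that item adds lucky guesses to real awareness, and adds more of them in the group with lower awareness. That pulls the two task groups together, which is the comparison H_B concerns. In a study meant to generate hypotheses, the size and direction of this estimate are the main product.

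Two lesser matters affect the same analysis. The scenario allocation is not what the text describes, and the reference values for magnitude recall do not match the programmed display.

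**Working it through.** The plan gives no chance level, awareness rate, sample size or alpha, so there is no figure of its own to reproduce.

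**Which item is meant.** The sections point both ways. The Structure table assigns immediate trend recall to the verbal review and quantification to the questionnaire, which favours the verbal item. The neighbouring measure, no trend in other parameters, can come only from the written form, which favours item 1. The text does not settle it.

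**Chance level of the verbal item.** The list has 10 A and 10 B rows. For a guesser who says fall with probability b, P(correct) = 0.5b + 0.5(1 - b) = 0.5 for any b. Randomising the direction stops a fixed answer from always being right; it does not bring a two-option item below 50%. If none of 20 participants noticed and all answered, 10 correct are expected (95% binomial range 6 to 14).

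**Effect on the task difference.** Let p be true awareness and f the share of non-observers who answer:

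observed = p + f(1 - p)/2 = p(1 - f/2) + f/2

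With the same f in both groups, the difference is multiplied by (1 - f/2). The awareness rates below are assumptions:

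| Awareness, technical second vs administrative second | f = 0 | f = 0.5 | f = 1 |
|---|---|---|---|
| 20% vs 70% | 20 vs 70 (50 points) | 40 vs 77.5 (37.5) | 60 vs 85 (25) |
| 30% vs 60% | 30 vs 60 (30 points) | 47.5 vs 70 (22.5) | 65 vs 80 (15) |

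**Unequal f.** Write fT and fA for the technical-second and administrative-second groups. For 30% vs 60% the observed difference is 0.30 + 0.20 fA - 0.35 fT. It turns negative only if fT exceeds 0.30/0.35 = 0.86 and fA is below (0.35 - 0.30)/0.20 = 0.25. At fT = 1 and fA = 0 it is 65% vs 60%. For 20% vs 70% it is 0.50 + 0.15 fA - 0.40 fT, which is never negative.

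**Scenario list.** Counts of task order by scenario:

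| | Administrative first, A | Administrative first, B | Technical first, A | Technical first, B |
|---|---|---|---|---|
| Consultant | 6 | 4 | 4 | 6 |
| Other | 5 | 5 | 5 | 5 |
| Total | 11 | 9 | 9 | 11 |

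Administrative first means technical second. If numbers run within role and all slots fill, falls are therefore 11/20 with technical second and 9/20 with administrative second. Of the 6 possible task orders in a block of 4, 2 line up fully with A, B, A, B (one in each direction) and 4 are balanced, so the expected imbalance is zero. If a fall were 30 points easier to notice than a rise (an assumption), the spurious task difference would be (0.55 - 0.45) x 0.30 = 0.03, or 3 points.

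**Reference pressures for magnitude recall.**

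| | Low | High | Systolic | Diastolic | Mean |
|---|---|---|---|---|---|
| Scenarios A and B, Events during the task | 75/48 (55) | 90/50 (63) | 15 | 2 | 8 |
| Monitor trend perception analysis | 70/48 (55) | 90/50 (65) | 20 | 2 | 10 |

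The analysis section scores against 20 systolic and 10 diastolic. Its own pressures give a diastolic change of 50 - 48 = 2; the 10 equals its change in mean, 65 - 55. If the display follows the scenario text, a participant who recalls the 15 mmHg systolic change exactly is given an error of (15 - 20)/20 = -25%. Both 15 and 20 are options on the verbal size question, so the right answer there is also unsettled.

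**The case against.** The forced choice is deliberate. A two-option cued question with a known 50% chance level is a legitimate way to reach unsure observers, and the plan did consider guessing. That stands: the question should be kept, and what is missing is a scoring and interpretation rule.

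The verbal question is conditional and no answer is demanded, so some non-observers will decline. That also stands, and it makes f = 1 a worst case. But the plan has no way to record or count a refusal.

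The study is a pilot that disclaims power. This excuses imprecision, so no power argument is made here. It does not excuse an undefined score.

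A reader might infer that the primary outcome as a whole is undefined or has a 50% floor. The documents do not support that. Correct identification is one of several measures. The open yes/no question is asked first and is free of this guessing, although it does not show that blood pressure was what was noticed or that the direction was right. The floor arises only if the verbal item is scored and non-observers answer.

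A reader might also infer that guessing could reverse the task effect. That needs near-complete answering by non-observers in one group and little in the other, and nothing in the documents suggests such a split.

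Finally, the alternating scenario might be read as confounding task with trend direction. Task order is block-randomised separately, so the documents show only predictability and a small chance imbalance.

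**Conclusion.** The point holds for one measure of the primary outcome: its scoring item and the handling of non-committal answers are not stated. If the verbal item is scored and a common share f of non-observers answers, the task difference shrinks by the factor (1 - f/2), down to half at f = 1. The factor follows from the design; the awareness rates and f are assumptions. Written item 1 already collects a better score, so the gap can be closed without new data. It is worth correcting but does not leave H_B without a usable measure.

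The alternating list departs from the stated randomisation but is minor: 11/20 against 9/20 falls, and about 3 points under the assumed 30-point effect. The mismatch in reference pressures is a separate inconsistency that directly affects the percentage errors for magnitude recall.

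**What to change.** **Scoring.** Keep the question order. State that correct identification is scored on written item 1, with all participants in the denominator and *Stayed the same*, *I don't recall* and blanks counted as not identified. Report it beside the open yes/no proportion. Report the verbal rise/fall answer separately against 50% chance, overall and split by the open yes/no answer. State that item 1 follows the leading verbal questions and can still be guessed.

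The cost is a few sentences. The downside is that an unsure observer who ticks *I don't recall* counts as not identified; the separate verbal report keeps that information. Moving item 1 ahead of the verbal question is not advised, since it would replace one priming order with another.

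**Scenario list.** If recruitment has not begun, regenerate the list so that each block of 4 within role holds the four order-by-scenario combinations once, in random order. If it has begun, keep the list, describe the allocation as alternating, and show the task comparison by scenario descriptively; cells would hold about 10 at most.

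**Pressures.** Reconcile Events during the task with Monitor trend perception analysis, including the 10 mmHg labelled diastolic, so that errors are computed against the values actually displayed.
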